8.1.5 HIV Resistance Analyses

In a subject being evaluated for failure to maintain HIV virologic suppression, if the confirmatory plasma HIV RNA level is ≥ 500 copies/mL, the subject's HIV PR, RT, and/or IN sequences, as applicable, will be analyzed by Monogram Biosciences using the GenoSure® Prime drug resistance assays. The number of subjects who demonstrate HIV genotypic resistance and the genotypic resistance mutations detected in the samples obtained from these subjects will be tabulated and summarized. Resistance will be defined as described by the IAS-USA Panel.¹⁹

8.1.6 Safety

Safety summaries will be provided overall (i.e., across study drug durations). All subjects who receive at least one dose of study drug will be included in the safety analyses.

8.1.6.1 Adverse Events

Adverse events will be coded using the Medical Dictionary for Regulatory Activities (MedDRA). The number and percentage of subjects with treatment-emergent adverse events (i.e., any event that begins or worsens in severity after initiation of study drug through 30 days post-study drug dosing) will be tabulated by primary MedDRA System Organ Class (SOC) and preferred term. The tabulation of the number of subjects with treatment-emergent adverse events by severity grade (Grades 1 – 5) and relationship to each study drug will also be provided. Subjects reporting more than one adverse event for a given MedDRA preferred term will be counted only once for that term using the most severe grade for the severity grade table and the most related for the relationship to study drug tables. Subjects reporting more than one type of event within a SOC will be counted only once for that SOC.

Additional analyses will be described in the statistical analysis plan.

8.1.6.2 Clinical Laboratory Data

Clinical laboratory tests will be summarized at each visit. The baseline value will be the last non-missing measurement prior to the initial dose of study drug. Mean changes from baseline to each post-baseline visit, including Final Treatment Visit, will be summarized descriptively. Changes from baseline to maximum post-baseline CTCAE grade of laboratory values will also be summarized.

8.1.6.3 Vital Signs Data

Mean changes in temperature, systolic and diastolic blood pressure, pulse, and weight from baseline to each post-baseline visit, including Final Treatment Visit, will be summarized descriptively. The number and percentage of subjects with post-baseline

values meeting pre-defined criteria for Potentially Clinically Significant (PCS) vital signs values will be summarized.

8.1.6.4 HCV/HIV Co-Infection

The following additional safety data will be summarized and analyzed for subjects with HCV/HIV co-infection overall:

- The percentage of subjects with plasma HIV RNA suppression at the end of treatment and at Post-Treatment Week 12 using the FDA Snapshot Algorithm;
- The number and percentage of subjects with plasma HIV RNA < 20 copies/mL at each applicable time point;
- Change from baseline in CD4+ T-cell count (absolute and percent) to each applicable post-baseline time point;
- Change from baseline in lymphocytes (count and percentage) and CD8+ T-cell counts (absolute and percent) to each applicable post-baseline time point;
- The listing of subjects with a plasma HIV RNA value ≥ 200 copies/mL at any baseline or post-baseline visit during the study.

The analysis of change from baseline in CD4+ T-cell count (absolute and percent), lymphocytes (count and percentage) and CD8+ T-cell counts (absolute and percent) will report the mean and median values at baseline and at each applicable post-baseline visit, as well as N, mean, median, standard deviation (SD), minimum and maximum values for the change from baseline overall.

8.1.7 Pharmacokinetic and Exposure-Response Analyses

Plasma concentrations of GLE, PIB, and their possible metabolites, if measured, will be tabulated for each subject and group. Summary statistics will be computed for each time and visit.

Plasma concentration data from this study may be combined with data from other studies and analyzed using the following general methodology:

Population pharmacokinetic analyses will be performed using the actual sampling time relative to dosing. Pharmacokinetic models will be built using a non-linear mixed-effect modeling approach with the NONMEM software (version VII, or higher version). The structure of the starting pharmacokinetic model will be based on the pharmacokinetic analysis of data from previous studies. Apparent oral clearance (CL/F) and apparent volume of distribution (V/F) of the PK analytes will be the pharmacokinetic parameters of major interest in the NONMEM analyses. If necessary, other parameters, including the parameters describing absorption characteristics, may be fixed if useful in the analysis. Once an appropriate base pharmacokinetic model (including inter- and intra-subject error structure) is developed, empirical Bayesian estimates of individual model parameters will be calculated by the posterior conditional estimation technique using NONMEM.

Relationship between exposure (noncompartmental or population pharmacokinetic model based values of concentrations over time, AUC, C_{trough} or some other appropriate measure of exposure) and clinical observations (antiviral activity or virologic end points, such as SVR₁₂ response) may be explored, if appropriate.

Exposure-response relationships for primary and secondary efficacy variables and/or some safety measures of interest may also be explored. Exposure response relationships will utilize a logistic regression analysis and/or a semi-mechanistic viral dynamic model. Additionally, relationship between exposure and safety endpoints of interest may also be explored. Additional analyses will be performed if useful and appropriate.

8.2 Determination of Sample Size

It is anticipated that a total of approximately 100 HCV infected treatment naïve GT1 – 6 subjects will be enrolled in this study. No formal hypothesis is being tested. If the observed SVR₁₂ rate in this study is 97% among 100 HCV GT1 – 6 treatment naive subjects, then the half-width of 2-sided 95% normal approximation interval is 3.3%.

8.3 Randomization Methods

This study is not randomized. Eligible subjects will be allocated to a treatment arm according to their cirrhosis status (presence/absence).

9.0 Ethics**9.1 Independent Ethics Committee (IEC) or Institutional Review Board (IRB)**

Good Clinical Practice (GCP) requires that the clinical protocol, any protocol amendments, the Investigator's Brochure, the informed consent and all other forms of subject information related to the study (e.g., advertisements used to recruit subjects) and any other necessary documents be reviewed by an IEC/IRB. The IEC/IRB will review the ethical, scientific, and medical appropriateness of the study before it is conducted. IEC/IRB approval of the protocol, informed consent and subject information, and/or advertising, as relevant, will be obtained prior to the authorization of drug shipment to a study site.

Any amendments to the protocol will require IEC/IRB approval prior to implementation of any changes made to the study design. The investigator will be required to submit, maintain, and archive study essential documents according to ICH GCP and all other applicable regulatory requirements.

Any serious adverse events that meet the reporting criteria, as dictated by local regulations, will be reported to both responsible Ethics Committees and Regulatory Agencies, as required by local regulations. During the conduct of the study, the investigator should promptly provide written reports (e.g., ICH Expedited Reports, and any additional reports required by local regulations) to the IEC/IRB of any changes that affect the conduct of the study and/or increase the risk to subjects. Written documentation of the submission to the IEC/IRB should also be provided to AbbVie.

9.2 Ethical Conduct of the Study

The study will be conducted in accordance with the protocol, International Conference on Harmonization (ICH) guidelines, applicable regulations and guidelines governing clinical study conduct and the ethical principles that have their origin in the Declaration of Helsinki. Responsibilities of the clinical investigator are specified in [Appendix A](#).

9.3 Subject Information and Consent

The investigator or his/her representative will explain the nature of the study to the subject, and answer all questions regarding this study. Prior to any study-related screening procedures being performed on the subject, the informed consent statement will be reviewed and signed and dated by the subject, the person who administered the informed consent, and any other signatories according to local requirements. A copy of the informed consent form will be given to the subject and the original will be placed in the subject's medical record. An entry must also be made in the subject's dated source documents to confirm that informed consent was obtained prior to any study-related procedures and that the subject received a signed copy.

Information regarding incentives for subjects and information regarding provisions for treating and/or compensating subjects who are harmed as a consequence of participation in the study can be found in the informed consent form.

10.0 Source Documents and Case Report Form Completion**10.1 Source Documents**

Source documents are defined as original documents, data and records. This may include hospital records, clinical and office charts, laboratory data/information, subjects' diaries or evaluation checklists, pharmacy dispensing and other records, recorded data from automated instruments, microfiches, photographic negatives, microfilm or magnetic media, and/or x-rays. Data collected during this study must be recorded on the appropriate source documents. The Investigator Awareness Date (SAE CRF) may serve

as the source for this data point. This adverse event data point required for eCRF completion can be entered directly in the eCRF.

The investigator(s)/institution(s) will permit study-related monitoring, audits, IEC/IRB review, and regulatory inspection(s), providing direct access to source data documents.

10.2 Case Report Forms

Case report forms (CRF) must be completed for each subject screened/enrolled in this study. These forms will be used to transmit information collected during the study to AbbVie and regulatory authorities, as applicable. The CRF data for this study are being collected with an electronic data capture (EDC) system called Rave® provided by the technology vendor Medidata Solutions Incorporated, NY, USA. The EDC system and the study-specific electronic case report forms (eCRFs) will comply with Title 21 CFR Part 11. The documentation related to the validation of the EDC system is available through the vendor, Medidata, while the validation of the study-specific eCRFs will be conducted by AbbVie and will be maintained in the Trial Master File at AbbVie.

The investigator will document subject data in his/her own subject files. These subject files will serve as source data for the study. All eCRF data required by this protocol will be recorded by investigative site personnel in the EDC system. All data entered into the eCRF will be supported by source documentation.

The investigator or an authorized member of the investigator's staff will make any necessary corrections to the eCRF. All change information, including the date and person performing the corrections, will be available via the audit trail, which is part of the EDC system. For any correction, a reason for the alteration will be provided. The eCRFs will be reviewed periodically for completeness, legibility, and acceptability by AbbVie personnel (or their representatives). AbbVie (or their representatives) will also be allowed access to all source documents pertinent to the study in order to verify eCRF entries. The principal investigator will review the eCRFs for completeness and accuracy and provide his or her electronic signature and date to eCRFs as evidence thereof.

Medidata will provide access to the EDC system for the duration of the trial through a password-protected method of internet access. Such access will be removed from investigator sites at the end of the site's participation in the study. Data from the EDC system will be archived on appropriate data media (CD-ROM, etc.) and provided to the investigator at that time as a durable record of the site's eCRF data. It will be possible for the investigator to make paper printouts from that media.

11.0 Data Quality Assurance

Computer logic and manual checks will be created to identify items such as inconsistent study dates. Any necessary corrections will be made to the eCRF.

12.0 Use of Information

Any research that may be done using optional exploratory research samples from this study will be experimental in nature and the results will not be suitable for clinical decision making or patient management. Hence, the subject will not be informed of individual results, should analyses be performed, nor will anyone not directly involved in this research. Correspondingly, researchers will have no access to subject identifiers. Individual results will not be reported to anyone not directly involved in this research other than for regulatory purposes. Aggregate data from optional exploratory research may be provided to investigators and used in scientific publications or presented at medical conventions. Optional exploratory research information will be published or presented only in a way that does not identify any individual subject.

13.0 Completion of the Study

The investigator will conduct the study in compliance with the protocol and complete the study within the timeframe specified in the contract between the investigator and AbbVie. Continuation of this study beyond this date must be mutually agreed upon in writing by both the investigator and AbbVie. The investigator will provide a final report to the IEC/IRB following conclusion of the study, and will forward a copy of this report to AbbVie or their representative.

The investigator must submit, maintain, and archive any records related to the study according to ICH GCP and all other applicable regulatory requirements. If the investigator is not able to retain the records, he/she must notify AbbVie to arrange alternative archiving options.

AbbVie will select the signatory investigator from the investigators who participate in the study. Selection criteria for this investigator will include level of participation as well as significant knowledge of the clinical research, investigational drug and study protocol. The signatory investigator for the study will review and sign the final study report in accordance with the European Agency for the Evaluation of Medicinal Products (EMEA) Guidance on Investigator's Signature for Study Reports.

The end-of-study is defined as the date of the last subject's last visit.

Appendix A. Responsibilities of the Clinical Investigator

Clinical research studies sponsored by AbbVie are subject to the Good Clinical Practices (GCP) and local regulations and guidelines governing the study at the site location. In signing the Investigator Agreement in Section **14.0** of this protocol, the investigator is agreeing to the following:

1. Conducting the study in accordance with the relevant, current protocol, making changes in a protocol only after notifying AbbVie, except when necessary to protect the safety, rights or welfare of subjects.
2. Personally conducting or supervising the described investigation(s).
3. Informing all subjects, or persons used as controls, that the drugs are being used for investigational purposes and complying with the requirements relating to informed consent and ethics committees (e.g., independent ethics committee [IEC] or institutional review board [IRB]) review and approval of the protocol and amendments.
4. Reporting adverse experiences that occur in the course of the investigation(s) to AbbVie and the site director.
5. Reading the information in the Investigator's Brochure/safety material provided, including the instructions for use and the potential risks and side effects of the investigational product(s).
6. Informing all associates, colleagues, and employees assisting in the conduct of the study about their obligations in meeting the above commitments.
7. Maintaining adequate and accurate records of the conduct of the study, making those records available for inspection by representatives of AbbVie and/or the appropriate regulatory agency, and retaining all study-related documents until notification from AbbVie.
8. Maintaining records demonstrating that an ethics committee reviewed and approved the initial clinical investigation and all amendments.

9. Reporting promptly, all changes in the research activity and all unanticipated problems involving risks to human subjects or others, to the appropriate individuals (e.g., coordinating investigator, institution director) and/or directly to the ethics committees and AbbVie.
10. Following the protocol and not make any changes in the research without ethics committee approval, except where necessary to eliminate apparent immediate hazards to human subjects.

Appendix C. Study Activities – Treatment Period

Activity	Screening	Day 1^a	Wk 4	Wk 8 (Arm B Only)	EOT (Arm A and Arm B) or Premature D/C from Treatment^b
Informed Consent ^c	X				
Dispense/Review Study Drug Dosing Card	X	X (Dispense only)	X	X	X (Review only)
Medical History ^d	X	X			
Physical Exam ^e	X	X			X
Vital Signs, Weight, Height ^f	X	X	X	X	X
ECG	X				
Hematology/Chemistry ^g /Coagulation Panel	X	X	X	X	X
Pregnancy Test (serum [s] urine [u]) ^h	X (s)	X (u)	X (u)	X (u)	X (u)
Anti-HCV Ab, Anti-HIV Ab	X				
Hepatitis B Panel	X				
HCV Genotype and Subgenotype	X				
FibroTest or FibroScan [®] or Liver Biopsy ^j	X				
Concomitant Medication Assessment	X	X	X	X	X
Adverse Event Assessment ^k	X	X	X	X	X
Study Drug Dispensed		X	X	X ^k	
HCV RNA Samples	X	X	X	X	X
Study Drug Accountability and Review of Study Drug Adherence			X	X	X ^l
HCV Resistance Sample		X	X	X	X

Activity	Screening	Day 1 ^a	Wk 4	Wk 8 (Arm B Only)	EOT (Arm A and Arm B) or Premature D/C from Treatment ^b
Pharmacokinetic Samples ^m			X	X	X
Child-Pugh Score (cirrhotic subjects only) ⁿ	X				X
Clinical Assessment of Hepatic Decompensation (cirrhotic subjects only) ⁿ		X			
HCC Screening Liver ultrasound (cirrhotic subjects only) ⁿ	X				
Patient Reported Outcomes Instruments (PROS) ^o		X			X
Flow cytometry sample ^p	X	X			X
HIV RNA ^p	X	X	X	X	X

Wk = Week; EOT = End of treatment; D/C = Discontinuation

* The EOT visit can be at Week 8 or 12 in accordance with treatment duration as described in Section 5.1.

- All procedures to be performed prior to first dose.
- Subjects who prematurely discontinue during the Treatment Period should return to the site to complete the Premature D/C Visit Procedures (preferably prior to the initiation of any other anti-HCV therapy).
- Subjects need to sign an IRB/IEC approved informed consent for the study (prior to performing any Screening or study-specific procedures).
- A complete medical history will be taken at Screening and will be updated at the Study Day 1 Visit.
- A symptom-directed physical examination may be performed at any other visit, when necessary. Any significant physical examination findings after the first dose will be recorded as adverse events.
- Height will be measured at the Screening Visit only.
- Blood samples for serum chemistry tests should be collected following a minimum 8-hour fast prior to study drug intake (with the exception of the Screening Visit, which may be non-fasting).
- Pregnancy testing is not required for women not of childbearing potential as defined in Section 5.2.4.
 - For subjects who have not had a qualifying liver biopsy within the previous 24 months for subjects without cirrhosis or at any time for subjects with compensated cirrhosis) or a qualifying FibroScan® within the previous 6 months for subjects without cirrhosis or at any time prior to Screening for subjects with compensated cirrhosis).

- j. Subjects with a historical negative Liver Ultrasound, CT or MRI (within 3 months prior to screening) are not required to have a screening Liver Ultrasound performed. If additional Liver Ultrasound testing is required it should be completed as an unscheduled visit. A positive ultrasound result suspicious of HCC will be confirmed with CT scan or MRI. A liver ultrasound should be performed at the end of treatment visit if it has been 6 months or more since the historical evaluation.
- k. See specific information regarding adverse event collection in Section 6.1.1.1.
- l. Dispensation at Week 8 and Study Drug Accountability at Week 12 are only applicable to Arm B. Subjects should bring all study drug to every visit for the site to review adherence. However, the site will record the number of tablets returned only at the Study Drug Accountability Visits at Weeks 4, 8, 12 (if applicable) or Premature D/C.
- m. PK samples will be collected at each scheduled study visit. Detail regarding timing of samples is provided in Section 5.3.2.1.
- n. Child-Pugh Score, Clinical Assessment of Hepatic Decompensation, and Liver Ultrasound are only performed for subjects in Arm B as described in Section 5.3.1.1.
- o. PROs should be administered before any study procedures in the order listed in Section 5.3.1.1. TSQM will be the only PRO not administered at Day 1.
- p. For HCV/HIV co-infected subjects.

Appendix D. Study Activities – Post-Treatment (PT) Period

Activity	PT Wk 4	PT Wk 12	PT D/C ^a
Vital Signs and Weight	X	X	X
Hematology/Chemistry/Coagulation Panel	X	X ^b	X ^c
Pregnancy Test (urine) ^d	X (u)	X ^e	X (u) ^c
Concomitant Medication Assessment ^e	X	X ^e	X ^e
Child-Pugh Score (cirrhotic subjects only)		X	X
Adverse Event Assessment ^f	X ^f	X ^g	X ^g
HCV RNA Samples	X	X	X
HCV Resistance Sample	X	X	X
Patient Reported Outcomes Instruments (PROs) ^h		X	X
Flow cytometry sample ^h	X	X	X
HIV RNA ⁱ	X	X	X
HCC Screening: Liver Ultrasound ^j		X	X

Wk = Week; PT D/C = Post-Treatment Discontinuation

- Subjects who prematurely discontinue from the Post-Treatment Period should return to the site to complete the PT D/C Visit procedures.
- Chemistry/Coagulation panel will only be collected at PT Wk 12 for subjects in Arm B (compensated cirrhosis).
- Hematology/Chemistry/Coagulation Panel and Pregnancy Test are not required at PT Wk 12, but only at PT D/C if subject discontinues prior to PT Wk 4.
- Women of childbearing potential do not require pregnancy testing beyond PTW4. Pregnancy testing will be performed at PT D/C visit only if the subject discontinues prior to PTW4. Pregnancy testing in PT Period is not required for females of non-childbearing potential as defined in Section 5.2.4.
- Only medications taken for SAEs and treatment of HCV will be collected after 30 days post-dosing.
- Nonserious AEs and all SAEs will be collected until 30 days post dosing. All spontaneously reported SAEs will be collected thereafter. See specific information regarding adverse event collection in Section 6.1.4.

- g. Only SAEs will be collected thereafter as described in Section [6.1.4](#).
- h. PROs should be administered before any study procedures in the order listed in Section [5.3.1.1](#).
- i. For HCV/HIV co-infected subjects.
- j. HCC Screening Liver Ultrasound performed only subjects in Arm B as described in Section [5.3.1.1](#).

Note: Day 1 of the Post-Treatment Period will be defined as the day after the last dose of study drug.

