HBsAg, anti-HBc and anti-HBs, anti-HCV Ab and anti-HIV Ab testing will be performed at Screening. HBV DNA testing may be performed to exclude occult HBV infection.

The investigator must discuss any local reporting requirements to local health agencies with the subject. The site will report these results per local regulations, if necessary. The HIV results will not be reported by the central laboratory to the clinical database.

Liver Diagnostic Testing

Subjects will be considered to be without cirrhosis or with cirrhosis based on the definitions below:

Without Cirrhosis (F2 and F3)

- A liver biopsy within 24 months prior to or during Screening demonstrating the absence of cirrhosis, e.g., a METAVIR, Batts-Ludwig, Knodell, IASL, Scheuer, or Laennec fibrosis score of 2 – 3, Ishak fibrosis score of 3 or 4; or
- A FibroScan® score of 8.8 to < 12.5 kPa within \leq 6 months of Screening or during Screening period (FibroScan® must be approved by the local regulatory agency to qualify for entrance criteria); or
- A Screening FibroTest score of 0.49 to 0.72 (inclusive).¹⁸

With Cirrhosis (F4)

- Previous histologic diagnosis of cirrhosis on liver biopsy, e.g., METAVIR, Batts-Ludwig, Knodell, IASL, Scheuer, or Laennec fibrosis score of > 3, Ishak score of > 4 or on a liver biopsy conducted during Screening; or
- A FibroScan® score of \geq 12.5 kPa within \leq 6 months of Screening or during Screening period (FibroScan® must be approved by the local regulatory agency to qualify for entrance criteria); or
- A Screening FibroTest result that is \geq 0.73.

The result of the liver biopsy supersedes the results of FibroScan and FibroTest and result of FibroScan supersedes the results of FibroTest. At Screening, it is recommended that subjects should otherwise meet all other inclusion criteria and none of the exclusion criteria before undergoing a liver biopsy.

Subjects with cirrhosis will be defined as having compensated cirrhosis if the Child-Pugh Score at screening is ≤ 6 .

Child-Pugh Score and Category

All subjects with cirrhosis will have Child-Pugh scores assessed at screening. The Child-Pugh score uses five clinical measures of liver disease (3 laboratory parameters and 2 clinical assessments) as shown in [Table 6](#). Child-Pugh score will be determined at the visits indicated in [Appendix C](#) and [Appendix D](#).

Table 6. Child-Pugh Classification of Severity of Cirrhosis

Parameter	Points Assigned for Observed Findings		
	1	2	3

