8.0 Statistical Methods and Determination of Sample Size

8.1 Statistical and Analytical Plans

An interim data lock may occur in the study if interim study results are needed for regulatory interaction purposes. No changes to the study design or treatment of subjects would result from this interim analysis; therefore, no adjustment for multiplicity is needed.

SAS® (SAS Institute, Inc., Cary, NC) for the UNIX operating system will be used for all analyses. All confidence intervals will be two-sided with an alpha level of 0.05.

Descriptive statistics will be provided, such as the number of observations (N), mean, and standard deviation (SD) for continuous variables and counts and percentages for discrete variables.

Safety and demographic analyses will be performed on all subjects who receive at least one dose of study drug.

Efficacy analyses will be performed on the intention-to-treat (ITT) population defined as all enrolled subjects who receive at least one dose of study drug, unless otherwise specified.

Sensitivity analyses of the primary efficacy endpoint, when applicable, will be performed on the intention-to-treat population modified to exclude subjects who did not achieve SVR₁₂ for reasons other than virologic failure (mITT-VF).

No data will be imputed for any efficacy or safety analysis except for analyses of SVR endpoints (HCV RNA data). HCV RNA values will be selected for the analyses of all SVR endpoints (e.g., SVR₄ and SVR₁₂) based on defined visit windows. A backward imputation method will be used to impute missing responses for SVR analyses.

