Scheduled Visit ^a	Nominal Day (Study Drug End Day)	Time Window (Study Drug End Day Range)
Post-Treatment Week 4	28	3 to 56
Post-Treatment Week 12	84	57 to 126
SVR ₄ ^b	28	3 to 56
SVR ₁₂ ^b	84	57 to 126

a. Post-Treatment Visits are applicable for subjects who received at least one dose of study drug.

b. For SVR windows, the last value in the window will be used.

Note: The result closest to the scheduled time point will be used, except for SVR₄ and SVR₁₂. For all windows, data must occur after Study Drug End Day 2. Study Drug End Day 0 is defined as the day of the last dose of study drug.

Table 3. Analysis Time Windows for Safety Laboratory and Vital Sign Measurements, Child Pugh Scores and PRO Instruments (Post-Treatment Period)

Scheduled Visit ^a	Nominal Day (Study Drug End Day)	Time Window (Study Drug End Day Range)
Post-Treatment Week 4	28	3 to 56
Post-Treatment Week 12	84	57 to 999
Final Post-Treatment Visit ^b	> 2 days after last dose of study drug	

a. Post-Treatment Visits are applicable for subjects who received at least one dose of study drug.

b. The last value within the Post-Treatment Period window will be used to define the Final Post-Treatment visit value. The lower bound of this Final window is Study Drug End Day 3. Study Drug End Day 0 is defined as the day of the last dose of study drug.

Note: The result closest to the scheduled time point will be used. For all windows, data must occur after Study Drug End Day 2. Vital signs are collected at every post-treatment visit; hematology, chemistry and coagulation panels are collected at PTW4 or PT D/C (if subject discontinued prior to PTW4). PRO instruments and Child Pugh Scores are collected at PTW12 (or PT D/C).

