11.5 Analysis of Child-Pugh Score

For subjects with compensated cirrhosis, Child-Pugh scores will be categorized as 5, 6, > 6, or missing at baseline and each protocol-specified post-baseline visit, including applicable post treatment visits. Shift tables from baseline to each post-baseline visit will

be created for the cirrhotic subjects in the safety population. The shift tables will cross-tabulate the frequency of subjects with baseline values in each category versus the post-baseline categories. For each baseline category and across the baseline categories, the percentage of subjects in each post-baseline category (excluding the post-baseline category of missing) will be calculated.

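### Arm B subjects who attend a PT D/C visit after PT Wk 4 are due a Child-Pugh score with no bilirubin, albumin or INR scheduled; separately, Table 5 marks PT/INR as Screening-only

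*Protocol*

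**What the plan says.** - **Schedule.** In Protocol Appendix D the row beginning "Child-Pugh Score (cirrhotic subjects only" is marked at PT Wk 12 and at PT D/C, and no footnote limits the PT D/C mark by time. Protocol 5.1.3 sends subjects who leave during follow-up to that visit.
- **Laboratory panels.** The PT Wk 12 mark carries footnote b: "Chemistry/Coagulation panel will only be collected at PT Wk 12 for subjects in Arm B (compensated cirrhosis". The PT D/C mark carries footnote c, under which the panels and the pregnancy test "are not required at PT Wk 12, but only at PT D/C if subject discontinues prior to PT Wk 4". Footnote c makes no exception for Arm B.
- **Components.** Protocol 5.3.1.1: "The Child-Pugh score uses five clinical measures of liver disease (3 laboratory parameters and 2 clinical assessments". Table 6 names the laboratory three as total bilirubin, serum albumin and INR.
- **SAP windows.** The note to SAP Table 3 (Section 6.2) says "hematology, chemistry and coagulation panels are collected at PTW4 or PT D/C (if subject discontinued prior to PTW4", then places Child-Pugh at PT Wk 12 or PT D/C. The Table 3 windows are Study Drug End Days 3 to 56 for PT Wk 4 and 57 to 999 for PT Wk 12.
- **SAP analysis.** Under SAP 11.5, "Child-Pugh scores will be categorized as 5, 6, > 6, or missing at baseline and each protocol-specified post-baseline visit", and in the shift tables "the percentage of subjects in each post-baseline category (excluding the post-baseline category of missing) will be calculated". Protocol 8.1: "No data will be imputed for any efficacy or safety analysis except for analyses of SVR endpoints (HCV RNA data".
- **INR.** In Protocol Table 5 the PT/INR entry carries footnote a, which restricts a test to Screening. Appendices C and D schedule coagulation panels at later visits, and SAP 11.3.1 lists INR among the parameters summarized.

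**The concern.** Followed as written, the plan asks a site for a score that it has not scheduled the blood tests to produce. Neither document says that PT Wk 4 laboratory values may be combined with a clinical assessment made at a later PT D/C visit, and the Protocol bars imputation of safety data, so the score would be missing.

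The subjects concerned are the cirrhotic ones, at a time when few other checks are scheduled: from 30 days after dosing, Protocol 6.1.4 collects only spontaneously reported serious adverse events. A subject whose bilirubin, albumin or INR had deteriorated would be counted as missing, not as > 6, and would drop out of the percentages. The Table 5 marker raises a separate question about one of the three laboratory inputs.

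**Working it through.** The plan states no figure on this point, so there is none to reproduce. The check sets the schedule side by side and then sizes the gap.

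**1. Arm B schedule, Appendix D**

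| Visit | Child-Pugh due | Chemistry and coagulation scheduled |
|---|---|---|
| PT Wk 4 | no | yes |
| PT Wk 12 | yes | yes (footnote b) |
| PT D/C before PT Wk 4 | yes | yes (footnote c) |
| PT D/C after PT Wk 4 | yes | no (footnote c) |

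Only the last row is in conflict.

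**2. Where such a visit falls in the SAP.** Nominal PT Wk 4 is Day 28 and nominal PT Wk 12 is Day 84. The interval after PT Wk 4 is 84 − 28 = 56 days, in two halves:
- Days 29 to 56 (56 − 28 = 28 days) lie in the PT Wk 4 window. A score from such a visit could not fill the PT Wk 12 row even with a full panel. The only scheduled laboratory values in that window are those from PT Wk 4 itself.
- Days 57 to 84 (84 − 56 = 28 days) lie in the PT Wk 12 window. No scheduled laboratory value falls there for a subject who leaves at PT D/C.

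**3. What the missing items do to the score.** Each item scores 1 to 3. With no ascites and no encephalopathy (2 points) and three laboratory items unknown, the total runs from 2 + 3 × 1 = 5 to 2 + 3 × 3 = 11, which covers all three scored categories (5, 6, > 6). With INR alone missing and the other four items at 1, it runs from 4 + 1 = 5 to 4 + 3 = 7, again all three. If the two clinical items already total 4, the minimum is 4 + 3 = 7, so the subject is > 6 whatever the laboratory shows. What is lost is mainly worsening seen in the laboratory values.

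**4. How many subjects.** Arm B has at most about 20 subjects (Protocol 5.1). The documents give no rate of leaving between PT Wk 4 and PT Wk 12, so the share p is an assumption. The expected number is 20p and the chance of at least one is 1 − (1 − p)^20.

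| Assumed p | Expected leavers | Chance of at least one |
|---|---|---|
| 1% | 0.2 | 18% |
| 2% | 0.4 | 33% |
| 5% | 1.0 | 64% |
| 10% | 2.0 | 88% |

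These are upper bounds for each p, because they count everyone who leaves. Footnote c matters only for those who leave and also attend a PT D/C visit.

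For rough orientation, Protocol Table 2 gives 2256 − 2206 = 50 non-responders among treatment-naïve and TE-PRS subjects. The resistance text in Section 3.0 gives 23 virologic failures, leaving 27, or 27/2256 = 1.2%, for other reasons. Among cirrhotic subjects, non-response for any cause is 281 − 274 = 7, or 7/281 = 2.5%. Neither is a dropout rate for this interval. Applied to 20 subjects they give 20 × 0.012 = 0.24 and 20 × 0.025 = 0.5.

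**5. Effect on the shift table.** One missing score reduces the row across baseline categories from 20 to 19, so each remaining subject is 1/19 = 5.3%. Rows within a baseline category depend on counts not yet known.

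**The case against.** The best defence is that the Protocol sets a floor. The text above Table 5 describes its tests as a minimum, Section 5.3.1.1 says Child-Pugh is to be determined at the Appendix D visits, and a panel that is not required is not forbidden. Protocol 5.4.1 asks for follow-up of unresolved laboratory abnormalities, and SAP 11.3 uses local laboratory values in all analyses. The SAP also already mixes sources: baseline Child-Pugh combines Day 1 clinical findings with baseline laboratory values (SAP 7.1).

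This shows that a score might be obtained. It does not close the gap: nothing requires the three tests to be drawn at this visit, and the baseline rule has no post-baseline counterpart.

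Four stronger readings are tempting and should be resisted:
- *All 56 days cost PT Wk 12 scores.* They do not; a visit on Days 29 to 56 belongs to the PT Wk 4 window whatever footnote c says.
- *Footnote c cancels the Arm B panel at PT Wk 12.* Its wording clashes with footnote b, but footnote c is attached to the PT D/C mark. Footnote b, which came in with the Arm B panel in Amendment 1, governs PT Wk 12. The clash has no effect on results by itself.
- *The SAP Table 3 note loses the Arm B PT Wk 12 values.* The note omits that panel, but the 57 to 999 window would capture it.
- *INR was not measured after Screening.* Read literally, the Table 5 marker would leave every post-screening Child-Pugh score uncalculable. But the text above the table sends its tests to the Appendix C and D visits, where coagulation panels are marked, so INR was probably collected. The marker appears in all three protocol versions in the file, so it is unlikely to be a one-off reading slip.

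**Conclusion.** The inconsistency is real in the current Protocol and is repeated in the SAP, and it is minor. An Arm B subject who attends a PT D/C visit after PT Wk 4 is due a Child-Pugh score with no scheduled bilirubin, albumin or INR. For the PT Wk 12 row this concerns Days 57 to 84. For Days 29 to 56 the open question is whether the PT Wk 4 panel may be used.

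The likely number affected is 0 or 1 of about 20. That rests on the enrollment cap and on an assumed low rate of leaving, which the documents do not state. Only the SAP 11.5 safety summary is touched; SVR12, OTVF and relapse do not use Child-Pugh. The Table 5 marker is a separate contradiction, most probably a labelling error, that would matter only if a site or laboratory followed it literally.

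**What to change.** - **Protocol Appendix D, footnote c.** State that Arm B subjects have chemistry and coagulation, including INR, at any PT D/C visit where Child-Pugh is due. Limit the statement that the panels are not needed at PT Wk 12 to Arm A. Leave the pregnancy-test part as it is.
- **SAP 6.2, Table 3 note.** Add the Arm B panels at PT Wk 12 and at PT D/C.
- **Protocol Table 5.** Remove footnote a from PT/INR, and state that the coagulation panel means PT/INR plus aPTT wherever it is marked.

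The cost is three wording changes and one extra laboratory panel for the few Arm B subjects who attend PT D/C after PT Wk 4. Blood for HCV RNA is already drawn at that visit.
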